#### 10.5.1.1 Subgroup Analyses

NOTE: These analyses are not planned due to the early termination of the trial but may be performed as exploratory if deemed worthwhile by the sponsor.

The analyses may be performed for subgroups of interest such as subgroups based on key demographic or clinical characteristics, e.g., gender, age group (< 65 years and >= 65 years of age), AChEI usage, and GBA genotype. The subgroup analyses will be applied to the mITT population.

No subgroup analyses are planned due to limited subjects enrolled in this study.

Confidential Page 36 of 57

## 10.5.2 Secondary Analysis

NOTE: The following description for the secondary analyses was prepared to implement the intention of the protocol, however in view of the early stopping of the trial this analysis will not be performed, unless the simple summary statistics suggest a finding of interest, in which case these would be performed as exploratory analysis.

The separate key secondary variables ADAS-Cog13 and ERP P300 latency will be analyzed using the MMRM model. Change form baseline ADAS-Cog13 score and change form baseline ERP P300 latency will be used as the outcome variable and the following fixed terms: baseline value, treatment arm, visit, treatment by visit interaction, baseline by visit by treatment interaction, GBA genotype, and baseline age. in the MMRM model. Similar summary statistics will be presented that was used for analysis of the primary endpoint. If MMRM model do not converge, active treatment and placebo groups will be compared using one sided t-test 2.5% significance level at Week 26 for change for baseline secondary variables.

Confidential Page 37 of 57

### 10.5.5 Interim Analysis

An interim analysis was planned to be performed when at least 30 subjects had completed the Week 2 visit. The analysis would have focused on the ERP P300 results and would be used to determine whether one or other of the 2 active doses of ATH-1017 (40 mg or 70 mg) is superior to the other (difference of 2 standard deviations). Based on the analysis, subjects would be enrolled with the superior dose.

In view of the early stopping of the trial, no interim analysis will be performed.

## 10.5.6 Final Analysis

This is an early closure study; other than summary statistics, all analyses are optional.

## 10.6 Safety and Tolerability

All safety analyses will be performed on the safety population.

#### **10.6.1** Adverse Events

All adverse events will be coded using the most current version of the Medical Dictionary for Regulatory Activities (MedDRA). A treatment-emergent adverse event (TEAE) is defined as any adverse event that begins or worsens in severity on or after the first study drug dose date until follow-up period. Treatment Related AE includes probably related, possibly related or related AEs. Injection Site Reactions will be identified from high level term (HLT) as 'Injection Site Reactions'.

The number and percentage of subjects experiencing one or more adverse events in the following adverse event categories will be summarized for each treatment group, and overall. No comparisons of treatment groups will be performed.

- Any AE
- Any TEAE
- Any Treatment Related TEAE (possibly related; probably related; related)
- Any severe TEAE

Confidential Page 38 of 57

- Any serious TEAE
- Any TEAE that led to discontinuation of study drug
- Any fatal TEAE
- All deaths

Treatment emergent adverse event (TEAE) incidence will be summarized and presented using primary MedDRA system organ classes (SOCs), and preferred terms (PTs).

- All TEAE
- Any Treatment Related-TEAE
- Study Drug Related Treatment-Emergent Adverse Events by Worst Severity
- Any serious TEAE by Worst Severity
- Any TEAE that led to discontinuation of study drug
- Treatment-Emergent Adverse Events Leading to Death
- Injection Site Reactions Treatment-Emergent Adverse Events

The following listings of adverse events will be prepared.

- All adverse events
- Drug Related Treatment-Emergent Adverse Events
- Injection Site Reactions Treatment-Emergent Adverse Events
- Serious Treatment-Emergent Adverse Events
- Treatment-Emergent Adverse Events Leading to Study Discontinuation
- Death listing

#### 10.6.2 Clinical Laboratory

Continuous blood clinical laboratory analytes observed values and change from baseline values will be summarized by analyte and visit using descriptive statistics (n, mean, median, SD, minimum, maximum) by treatment group. The denominators for calculating the percentages will be based on the number of subjects with non-missing assessments in each treatment group at a particular visit for the safety population. The latest non-missing clinical laboratory tests collected prior to dosing will be used as the baseline values.

Confidential Page 39 of 57

Clinical laboratory results will be provided in data listings by treatment group, subject, lab category, visit and parameter.

## 10.6.3 Electrocardiograms

ECG values will be summarized by visit and treatment group using descriptive statistics (n, mean, median, SD, minimum, maximum) for PR interval, QT interval, QTcB interval, QTcF interval, RR interval, mean heart rate, and QRS duration.

The latest non-missing ECG value collected prior to dosing will be used as the baseline value. The baseline values will usually be the vital signs recorded at the Day 1 30 min pre-dose visit. In the case of repeated ECG parameters, the last collected values within that visit will be used for the summary tables.

ECG will be provided in a data listing by subject, treatment group, subject, visit, timepoint and parameter.

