## 8.4 Safety Summaries

The Safety population will be used for analyses of each of the safety endpoints. All concomitant medications will be tabulated according to drug class and preferred term using the World Health Organization Drug dictionary. Clinical laboratory tests, vital signs, physical and neurological examinations, and ECG results will be summarized by number of subjects, frequency rates and by treatment group. The timepoint of each event will also be summarized.

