## 8.4.3 12-Lead Electrocardiogram

12-lead ECG data (observed and change from baseline) will be listed for each subject by visit. Observed values and change from baseline will be summarized descriptively.

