# 5.2 Secondary Objectives

- To evaluate the clinical efficacy of ATH-1017 separately on:
  - 1) Cognition and
  - 2) ERP P300 latency

Confidential Page 10 of 57

[figure not shown]
Table 1. Study Objectives and Associated Endpoints

Primary Objectives	Primary Endpoints	
To evaluate the clinical effects of ATH-1017 in subjects with PDD or DLB	The Global Statistical Test (GST) score (O'Brien, 1984) that combines the standardized change from baseline scores at Week 26 for cognition (Alzheimer's Disease Assessment Scale-Cognitive Subscale 13-item version [ADAS-Cog 13 ]) and ERP P300 latency, comparing ATH-1017 to placebo	
To determine the safety and tolerability of ATH-1017 in subjects with PDD or DLB	Analysis of adverse events (AEs), including injection site AEs; changes from baseline for the following variables: vital signs, 12-lead electrocardiogram (ECG), and laboratory tests (chemistry, hematology, urinalysis); concomitant medication assessments, physical and neurological exams, Columbia-Suicide Severity Rating Scale (C-SSRS), and Geriatric Depression Scale (GDS)	
Secondary Objectives	Secondary Endpoints	
To evaluate the clinical effects of ATH-1017 separately on: (1) cognition and (2) ERP P300 latency	
 
ADAS-Cog13 score: change from baseline at Weeks 2, 12, 20, and 26 compared to placebo
 
ERP P300 latency: change from baseline at Weeks 2, 12, and 26 compared to placebo
 
	

Confidential Page 11 of 57

Exploratory Objectives	Exploratory Endpoints

Confidential Page 12 of 57

Confidential Page 13 of 57

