#### 6 STUDY DESIGN CONSIDERATIONS

This study (ATH-1017-PD-0201) is designed to demonstrate as a safety and proof of concept study of ATH-1017 in PDD and DLB subjects. Eligible participants will receive once daily (OD) subcutaneous (SC) injections of ATH-1017 (40 mg or 70 mg) or placebo, over a 26-week double-blind period, followed by a 4-week safety follow-up.

NOTE: This study was stopped early; safety listings and summaries will be performed as previously envisioned; however efficacy and biomarker analyses will be exploratory in nature.

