## 10.6.5 Physical and Neurological Examination

The physical and neurological examination normal/abnormal results will be listed by treatment group, subject, visit and parameter.

[figure not shown]

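### The SAP omits the ECG and vital-sign change-from-baseline summaries and the ECG and examination counts that the safety endpoint or the protocol calls for, and does not specifically declare the reduction

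*SAP*

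**What the plan says.** SAP Table 1 (Section 5.2) defines the safety half of the primary endpoint as including "changes from baseline for the following variables: vital signs, 12-lead electrocardiogram (ECG), and laboratory tests". It also names physical and neurological examinations.

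The protocol's analysis sections match this. On ECG, Protocol 8.4.3 states: "Observed values and change from baseline will be summarized descriptively". Protocol 8.4 adds that "physical and neurological examinations, and ECG results will be summarized by number of subjects, frequency rates and by treatment group".

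The SAP's output sections are narrower. SAP 10.6.3 states that "ECG values will be summarized by visit and treatment group using descriptive statistics (n, mean, median, SD, minimum, maximum", and then that "The latest non-missing ECG value collected prior to dosing will be used as the baseline value", but no output in the section uses that baseline. SAP 10.6.4 is built the same way for vital signs: by-visit descriptive statistics and a defined baseline, with no mention of change. For the examinations, the whole of SAP 10.6.5 is: "The physical and neurological examination normal/abnormal results will be listed by treatment group, subject, visit and parameter".

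SAP Section 6 records that the study stopped early and says that "safety listings and summaries will be performed as previously envisioned". SAP Section 8, which lists changes from the protocol, opens with a general remark that analysis will be kept to a minimum. Its four items concern the interim analysis, alternative tests, the status of any test result, and optional exploratory and subgroup work. None mentions ECG, vital signs or examinations.

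**The concern.** Safety is a primary objective, and it is the part of the analysis that the SAP says survives early stopping intact. A programmer who follows the SAP as written would nevertheless produce no change-from-baseline table for ECG or vital signs, no subject counts for ECG and no summary of the examinations by arm. A reader of the study report could then not see, by arm, how far QTcF or blood pressure moved within subjects, how many subjects had a prolonged QTcF, or how many had a new abnormal examination finding. Because Section 8 does not name these reductions, nobody would know from the SAP that they had been made.

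**Working it through.** There is no stated figure to reproduce. The check is a comparison of sections.

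| Item | Endpoint (SAP Table 1) | Protocol analysis section | SAP output section | Gap |
|---|---|---|---|---|
| Blood laboratory tests, change | named | 8.4.2, by visit with shift tables | 10.6.2, observed and change | none on change |
| ECG, change | named | 8.4.3, observed and change | 10.6.3, values by visit | change not specified |
| ECG, subject counts and rates | not specified | 8.4 | 10.6.3, none | counts not specified |
| Vital signs, change | named | 8.4.2, by visit, change not named | 10.6.4, values by visit | change not specified |
| Physical and neurological examinations | named | 8.4, counts and rates | 10.6.5, listing | no summary specified |

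1. **Extent.** The endpoint names change from baseline for three variables. The SAP writes it out for one of them, so 3 - 1 = 2 have no specified change table.

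2. **Could the phrase used for ECG already include change?** SAP 10.6.2, the section immediately before, spells out both observed and change values for laboratory analytes. The shorter wording in 10.6.3 therefore cannot safely be read as covering both.

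3. **Can change be recovered from the observed-value tables?** No. If the SDs at baseline and at the visit are equal, SD of change = SD x sqrt(2(1 - r)), where r is the within-subject correlation. The documents give no r, and the tables would not show it. Taking r as an assumption, the factor is sqrt(1.4) = 1.18 at r = 0.3, sqrt(1.0) = 1.00 at r = 0.5 and sqrt(0.4) = 0.63 at r = 0.8. With dropout, the difference between visit means is also not the mean within-subject change.

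4. **What do the adverse event tables catch?** Under SAP 6.4.1.1 an abnormal safety assessment is an adverse event if the investigator judges it clinically significant. One associated with the underlying disease is not, unless judged more severe than expected. SAP 10.6.1 then tabulates treatment-emergent events by system organ class and preferred term. New abnormalities below that judgment appear in no specified count. The neurological examination covers mental status, tone and gait (SAP 6.4.7), where a new finding in PDD or DLB could plausibly be attributed to the disease.

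5. **Does the by-visit maximum protect against a missed QTcF excursion?** Only partly. ECGs are taken in triplicate (Protocol 6.4.6), and a prolonged QTcF calls for at least two repeats (Protocol 5.8). SAP 10.6.3 puts the last reading of the visit into the summary when a parameter is repeated. SAP 9.6 takes the last value in the window for non-efficacy data, with unscheduled visits included. Call the readings q1, q2, q3. If q1 > 500 msec and q3 is at or below 500 msec, the table carries q3 and the maximum need not show q1. Where the excursion is the last reading, the maximum shows that it occurred but not how many subjects had one.

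**The case against.** The best defence is that this is a drafting omission and not a decision. The SAP is based on Protocol v3.0, whose 8.4.3 contains the ECG change summary. SAP Section 6 keeps safety reporting as planned, and 10.6.3 and 10.6.4 define baselines that would serve little purpose otherwise. Section 10.6.3 even describes its ECG baseline as vital signs, which suggests text carried over from another section. This is plausible, and nothing in the documents shows an intention to drop the summaries. It does not remove the need to correct the SAP, because the tables are programmed from it.

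A reader might infer that a QTcF excursion or a cluster of neurological findings would be invisible in every planned output. The documents do not support that. The by-visit maximum is planned, ECG and examination results are listed, the investigator or a qualified designee evaluates every ECG, and clinically significant findings reach the treatment-emergent tables. A QTcF meeting the Protocol 5.8 criterion must also be reported to the Medical Monitor.

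A reader might also infer that the protocol promised a table of QTcF categories. It did not. The limits in Protocol 4.3 and 5.8 are for entry and stopping, and Protocol 8.4 asks only in general terms for counts and rates. Using those limits is one reasonable way to give that promise content.

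Finally, a reader might assume that one outlier must vanish in the arm mean. One subject with an assumed 70 msec rise moves the mean by 70/n, against a standard error of SD/sqrt(n). The shift is below one standard error only if n > (70/SD)^2, which is 12.25 at an assumed SD of 20 msec and 21.8 at 15 msec. The planned 25 per arm satisfies this, but 12 or fewer does not at either SD. The trial stopped early and actual arm sizes are not given. A mean of change would move by the same amount, so the argument would not support a change table anyway.

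The general remark that opens Section 8 is a partial declaration of reduced analysis, but it names none of these items and conflicts with Section 6.

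**Conclusion.** The point holds as a mismatch between the endpoint, the protocol and the SAP's specified outputs. Change from baseline is missing for two of the three variables for which the endpoint names it. ECG counts are missing, and the examinations have a listing in place of a summary. For ECG and the examinations the protocol plans what the SAP leaves out. For vital signs the conflict is with the endpoint, since Protocol 8.4.2 does not name change. The practical consequence is limited to two things: abnormalities not judged clinically significant have no specified count by arm, and a non-final QTcF excursion can be lost from the tabulated maximum.

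The conclusion rests on the text alone and on no assumed variance, correlation or arm size. No numerical effect is claimed. It should be corrected before the safety tables are produced, but it does not suggest that safety data are uncollected or unreported.

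**What to change.** - **SAP 10.6.3 and 10.6.4:** add change from baseline by visit and arm, using the baselines already defined there.
- **SAP 10.6.3:** add counts by arm of subjects with any post-dose QTcF at or above the protocol's entry limits (450 msec or more in males, 470 msec or more in females) and above 500 msec. Use all scheduled, repeat and unscheduled ECGs, including the Day 1 post-dose recording, and not the last value per visit or window. Label these as descriptive categories only, with no bearing on eligibility or stopping.
- **SAP 10.6.5:** add a count by body system and arm of subjects normal at baseline and abnormal at any later visit. The schedule places the Day 1 examination after dosing, so the baseline here is the Screening examination, as the general rule in SAP 9.2 also implies.
- **Otherwise:** state in SAP Section 8 which of these summaries are being dropped and why, and reconcile that with Section 6.

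The cost is SAP wording and a few extra tables. No new data are needed.

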CT = computed tomography; C-SSRS = Columbia-Suicide Severity Rating Scale; ECG = electrocardiogram; ECG = electrocardiogram; ERP = event-related potential; FSH = follicle-stimulating hormone; fT3 = free tri-iodothyronine; fT4 = free thyroxine; GDS = Geriatric Depression Scale; HR = heart rate; IMP = investigational medicinal product;

MOCA = Montreal Cognitive Assessment; MRI = magnetic resonance imaging; NMSS = Non-Motor Symptom Scale; PK = pharmacokinetic; SC = subcutaneous; TSH = thyroid-stimulating hormone.

- a If 28 days is not sufficient to complete the Screening period, the possibility of an extension can be discussed with the Medical Monitor.
- b Only weight collected at Baseline/Day 1 (Visit 2b), Week 12 (Visit 5), Week 26 (Visit 8), and Safety follow-up (Visit 9).
- c Urine pregnancy test will be performed for females with child-bearing potential at screening.
- d Blood collection for FSH levels (to confirm post-menopausal state in females), serology, genotyping, fT3, fT4, and TSH.
- e 'C-SSRS Baseline/Screening' version will be administered at Screening and 'C-SSRS Since Last Visit' version will be administered at all post-Screening visits.
- f Dispensing of kits containing study drug will occur every 2 weeks; drug returns will be recorded and compliance calculated. Larger provision of study drug is permitted to accommodate personal need, e.g., vacation; site should check in with subject/caregiver via phone approximately every 2 weeks in cases of larger dispensing. IMP administration by the caregiver will be assessed at Visits 2b through 8, inclusive.
- g First SC injection of IMP will be performed at site under supervision; subject should withhold IMP dose on the day of subsequent clinic visits (IMP administration will be done on site under supervision of site staff; training of proper injection techniques for subject/caregiver will be performed as needed); subjects will remain at site for 2 hours ± 15 minutes for safety observation follow up after first SC injection of IMP.
- h Physical and neurological exam to be done post-dose at all visits where subjects are dosed.
- i MRI (or CT) scan if not done since the initial diagnosis of PD.
- j 12-lead ECGs will be performed pre-dose and 30 (± 15) minutes post-dose on Day 1(Visit 2b) and 30 (± 15) minutes post-dose at all other visits. All ECG assessments will be performed in triplicate.

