- k Vital signs (systolic and diastolic BP, orthostatic BP, HR, respiratory rate, and body temperature) will be performed pre-dose on all visits. Supine BP and HR recordings will be made after the subject has been supine for at least 5 minutes. Orthostatic BP will be recorded as follows: the first blood pressure will be the average of 3 measurements recorded after the subject is supine for 5 minutes; the second blood pressure will be recorded after the subject stood for up to 3 minutes.
- 1 Safety labs include chemistry, hematology, urinalysis, and coagulation.
- m Prior and concurrent medications.
- n Subject hearing will be tested to establish suitability for ERP assessment (ability to hear or differentiate the 2 different tones necessary for auditory ERP P300 assessment, using the centrally provided ERP equipment); subjects who wear a hearing aid must remove their hearing aid during the Screening auditory test and during ERP P300 recordings.
- o ERP P300 will be performed at the Pre-baseline visit (Visit 2a, Day -10 to Day -3, no dosing); pre-dose and post-dose at Baseline/Day 1 (Visit 2b), Week 2 (Visit 3), Week 12 (Visit 5), and Week 26 (Visit 8). ERP P300 data should be uploaded for quality check immediately after the completion of the Pre-baseline visit (Visit 2a). ERP P300 will also be performed at Safety follow-up (Visit 9, no dosing).
  - Pre-dose ERP P300 assessments will be performed immediately preceding IMP dose but can be up to 1 hour before dose
    in clinic.
  - Post-dose ERP P300 assessments will be performed at approximately 2 (± 1) hours after dose.
- r Subjects who terminate prior to Visit 9 are to complete same assessments as Visit 8/ET (early termination). For clinical outcome assessments, if completed the assessment within 4 weeks of the ET visit they do not need to be repeated; all safety outcomes and drug accountability should be performed regardless of interval.
- \* At Baseline/Day 1 (Visit 2b), ADAS-Cog13 will be performed pre-dose. For visits after Baseline (except for Safety follow-up when dosing is not applicable), all cognitive assessments will be performed post-dose, in the order of ADAS-Cog13, assessments, with ADAS-Cog13 performed at approximately 1 hour (± 30 minutes) post dose.

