#### • ECG criterion:

QTcF > 500 msec (if prolonged QTcF interval is observed during the study, then a minimum of 2 repeat ECGs should be obtained over a brief period. The mean of the 3 ECGs will be used to determine this stopping criterion).

For QTcF readings that are borderline, or difficult to interpret due to e.g., presence of a branch bundle block, or in those where the T and U waves are superimposed or connected, a manual, local reading using the same ECG device should be considered to determine applicability of this ECG stopping criterion, in discussion with the Medical Monitor. Baseline conditions should be taken into account when considering the ECG stopping criterion (see Section 4.3, exclusion criterion #17).

In addition, if any of the above criteria are met, the event must be reported and discussed with the Medical Monitor.

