## 6.4.6 12-Lead Electrocardiogram

Standard safety 12-lead ECGs will be performed at Screening, at pre-dose and 30 ( $\pm$  15) minutes post-dose on Day 1 and 30 ( $\pm$  15) minutes post-dose at all other visits. All ECGs will be performed in triplicate, as detailed in the Schedule of Assessments (Table 1).

The 12-lead ECGs will be performed after the subject has been resting supine for  $\geq 5$  minutes. The ECG will include all 12 standard leads and a Lead II rhythm strip on the bottom of the tracing. The following ECG parameters will be collected: PR interval, QRS interval, RR interval, QT interval, and QTcF.

All ECGs must be evaluated by the investigator or qualified designee for the presence of abnormalities. Collection and analysis of ECG data will be performed by a central ECG vendor.

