#### 9.6 Visit Windows / Unscheduled Visits

Visit windowing will be applied for the analyses which use visit categories. For categorical visit summaries, all visits including early termination assessments and unscheduled visits will be included with the closest scheduled post-baseline visit that includes the efficacy or safety assessment, based on number of days since Day 1. For the primary variable of ERP P300 latency effect, if multiple assessments fall within the same analysis window, pre- and post-dose measurement will be averaged within the analysis window for this variable. For all other efficacy assessments, if multiple efficacy assessments fall within the same analysis window (other than baseline), any non-missing efficacy assessments will be averaged. For all non-efficacy assessments, a last-within-window approach will be used.

The analysis windows for ERP P300, ADAS-Cog13 and COWAT are:

	Protocol-Specified	Analysis-Specified
Analysis Visit	Day	Interval
Week 2	Day 14	Day 2-63
Week 12	Day 84	Day 64-112
Week 20	Day 140	Day 113-161
Week 26	Day 182	Day 162-196
Week 30	Day 210	Day 197-218

The analysis windows for C-SSRS, Physical and Neurological Exams, EG, Vital Signs, Labs are:

	Protocol-Specified	
Analysis Visit	Day	Analysis-Specified Interval
Week 2	Day 14	Day 2-28
Week 6	Day 42	Day 29-63
Week 12	Day 84	Day 64-98
Week 16	Day 112	Day 99-126
Week 20	Day 140	Day 127-161
Week 26	Day 182	Day 162-196
Week 30	Day 210	Day 197-218

The analysis windows for GDS are:

Confidential Page 32 of 57

	Protocol-Specified	
Analysis Visit	Day	Analysis-Specified Interval
Week 12	Day 84	Day 2-133
Week 26	Day 182	Day 134-196
Week 30	Day 210	Day 197-218

The analysis visit windows for MMSE is:

Analysis Visit	Protocol-Specified Day	Analysis-Specified Interval
Week 12	Day 84	Day 2-112
Week 20	Day 140	Day 113-161
Week 26	Day 182	Day 162-218

The analysis windows for MDS-UPDRS, NMSS, ADCS-ADL23, ADCS-CGIC, ADCS-CaGIC, ADCS-CGIS, and PK are:

Analysis Visit	Protocol-Specified Day	Analysis-Specified Interval
Week 12	Day 84	Day 2-133
Week 26	Day 182	Day 134-218

Confidential Page 33 of 57

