## 10.6.4 Vital Signs

Each vital sign will be summarized by treatment and by visit, using descriptive statistics (n, mean, median, SD, minimum, maximum) for the safety population for diastolic blood pressure, systolic blood pressure for both standing and supine position, heart rate and respiratory rate.

The latest non-missing vital sign value collected prior to dosing will be used as the baseline values. The baseline values will usually be the vital signs recorded at the baseline visit. In the case of repeated vital signs, the last collected values within that visit will be used for the summary tables.

Vital signs will be provided in a data listing by treatment group, subject, visit and parameter.

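### ECGs are planned in triplicate, but the SAP's last-value rules put only one reading of three into the summary tables and the baseline, adding avoidable noise

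*SAP*

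**What the plan says.** **Collection.** Footnote j of the protocol's Schedule of Assessments (Table 1) states: "All ECG assessments will be performed in triplicate". Protocol 6.4.6 repeats the requirement, and SAP Appendix 2 carries the same footnote. On Day 1 there is a pre-dose and a post-dose recording; other dosing visits have a post-dose recording.

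**Summary tables.** SAP 10.6.3 summarises each ECG parameter by visit and treatment group (n, mean, median, SD, minimum, maximum). It resolves multiple values as follows: "In the case of repeated ECG parameters, the last collected values within that visit will be used for the summary tables".

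**Baseline.** The same section says: "The latest non-missing ECG value collected prior to dosing will be used as the baseline value".

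**General rule.** SAP 9.6 adds: "For all non-efficacy assessments, a last-within-window approach will be used".

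**Status of the analysis.** ECG change from baseline is a component of the primary safety endpoint (Protocol 2; SAP Table 1), and Protocol 8.4.3 plans descriptive summaries of observed values and change. The note in SAP 6 keeps the safety listings and summaries in place despite the early stop.

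**The concern.** Triplicate recording is normally done so that the readings can be averaged, which reduces the short-term variation between them. Here the extra recordings are planned at every time point, but the stated rules select one of them and make no use of the other two in the tables. The choice affects change from baseline twice, because both the baseline and the post-dose value are single readings.

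What is at stake is the precision of the descriptive QTcF and other interval summaries. Enrolment was limited (SAP 9.5 and 10.5.1.1), and SAP 9.1 splits the safety tables further by disease type and by acetylcholinesterase inhibitor use within disease type. In small cells, an avoidably wide SD or an extreme value caused by one noisy reading makes a table harder to interpret.

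**Working it through.** The documents state no QTcF SD, no ECG precision target and no ECG-based sample size, so there is no figure to reproduce. The check has three parts.

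**1. How many planned readings reach the tables or the baseline.** Scheduled ECG time points (Table 1 and footnote j): Screening 1, Day 1 pre-dose and post-dose 2, Visits 3 to 8 6, Visit 9 1.

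- Time points: 1 + 2 + 6 + 1 = 10.
- Planned readings for a subject who completes: 10 × 3 = 30.
- Readings used, at one per time point: 10.
- Share left out: (30 − 10)/30 = 20/30 = 66.7%.

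**2. Whether any other rule rescues the triplicate.**

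| Provision | What it selects |
|---|---|
| SAP 10.6.3, tables | last value within the visit |
| SAP 10.6.3, baseline | latest non-missing pre-dose value |
| SAP 9.6, non-efficacy data | last value within the window |

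None of the three averages. The first is also framed per visit rather than per time point. On Day 1, read literally, it picks the post-dose recording for the visit, while the baseline sentence picks the pre-dose one.

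**3. Effect on the SD of change from baseline.** Let sw be the SD between replicates in one session, sb the within-subject SD between sessions, and m the number of readings averaged. Replicate errors are taken as independent with equal variance. Stable differences between subjects cancel in a change score, so

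Var(change) = 2 × (sb² + sw²/m).

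Let f = sw²/(sb² + sw²), the replicate share of the **within-subject** variance of a single reading. Then

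Var(mean of 3)/Var(single) = (1 − f) + f/3 = 1 − 2f/3, and the SD ratio is its square root.

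| f (assumed) | 1 − 2f/3 | SD ratio | Fall in SD |
|---|---|---|---|
| 0.10 | 0.933 | 0.966 | 3.4% |
| 0.25 | 0.833 | 0.913 | 8.7% |
| 0.50 | 0.667 | 0.816 | 18.4% |

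In milliseconds, with assumed SDs at the two ends of that range:

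- f = 0.10 (sw = 4, sb = 12): single reading √(2 × (144 + 16)) = 17.9 ms; mean of three √(2 × (144 + 16/3)) = 17.3 ms.
- f = 0.50 (sw = 8, sb = 8): single reading √(2 × (64 + 64)) = 16.0 ms; mean of three √(2 × (64 + 64/3)) = 13.1 ms.

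For observed values, as opposed to changes, the spread between subjects also enters the SD, so the proportional gain is smaller.

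**The case against.** **The wording may mean re-tests.** The protocol uses triplicate for the planned replicates and repeat for extra recordings after a prolonged QTcF (Protocol 5.8). SAP 10.6.3 speaks of repeated parameters, so it may have been written for unplanned re-tests. That is a fair reading of one sentence, but it does not settle the matter. The SAP would then have no specific rule for the triplicate, SAP 9.6 would still take the last value, and the baseline sentence does not depend on the word at all.

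**The central vendor may average.** Protocol 6.4.6 and SAP 6.4.6 give ECG collection and analysis to a central vendor. If it delivers one averaged value per time point, the last-value rule does no harm. Neither document says that it does. This remains the main uncertainty about practical effect.

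**The summaries are descriptive.** This stands. There is no ECG test, the trial stopped early, and a noisier SD reverses no conclusion.

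Four stronger readings may tempt a reader, and the documents do not support them:

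- *Two thirds of the ECG data are discarded.* The SAP 10.6.3 listing, by visit and time point, is not restricted to the last reading. The readings are left out of the tables and the baseline, not lost.
- *The tables contradict the stopping rule.* Protocol 5.8 says: "The mean of the 3 ECGs will be used to determine this stopping criterion". That is a confirmation step for one subject after a prolonged QTcF has been seen, and its three ECGs are not stated to be the planned triplicate. Group tables need not reproduce it.
- *Vital signs have the same defect.* SAP 10.6.4 does say: "In the case of repeated vital signs, the last collected values within that visit will be used for the summary tables". But footnote k of the protocol's Table 1 already defines the supine value: "the first blood pressure will be the average of 3 measurements recorded after the subject is supine for 5 minutes". SAP 6.4.4 says the same. The last-value rule reads naturally as applying to a repeat of that average.
- *The loss equals a stated number of extra subjects.* With no ECG test, no ECG-based sample size and no variance components, that translation has little meaning.

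**Conclusion.** The point holds for the ECG summary tables and baseline. As written, one reading in three is used where all three were planned. The direction is certain for any replicate variance above zero, provided the analysis dataset holds individual readings. The size cannot be fixed from the documents: it is a 3% to 18% lower SD of change if the replicate share of within-subject variance is between 10% and 50%, and it is small if variation between sessions dominates. Both the share and the independence of replicate errors are assumptions.

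This is a worthwhile, low-cost improvement to a component of the primary safety endpoint whose summaries are still to be produced. It does not threaten the trial's conclusions.

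**What to change.** In SAP 10.6.3:

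- Define the ECG value at each nominal time point as the mean of the available replicates, with Day 1 pre-dose and post-dose kept separate.
- Define baseline as the mean of the replicates at the latest pre-dose time point with non-missing data. This keeps a fallback for a subject whose Day 1 pre-dose recording is missing.
- Limit the last-value rule to unplanned repeats.
- Keep the individual readings in the listings.

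In SAP 9.6, exempt ECG triplicates from the last-within-window rule; otherwise the two sections would conflict.

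If the vendor already supplies a mean per time point, the SAP should say so, and the same definitions then only document it.

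Cost: a few sentences in the SAP and a short programming change. No new data, visits or recordings are needed.
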